While the increased risk of CV disease and morbidity associated with ADT has been established by large observational studies, the mechanism behind this risk remains unclear. However, increasing evidence has demonstrated that inflammatory immunity can play a central role in mediating cardiac damage, especially at the coronary vessel endothelium. Aim 1 will provide insight into anatomic/pathophysiologic mechanism of ADT-associated CV toxicity, testing our hypothesis that CV damage following ADT is due to accelerated coronary artery atherosclerosis and/or plaque instability associated with inflammatory immune responses. In Aim 2, we will evaluate peripheral blood samples (drawn at 3-, 6-, and 12-months and stored) from patients enrolled on study to determine how pre-existing or augmented inflammatory immunity impacts the risk of CV injury following ADT, testing the underlying hypothesis that ***pre-existing inflammatory immunity increases the risk of CV injury following ADT due to an immune-mediated effect of GNRHa but not antagonists***. These studies provide important mechanistic insight into how inflammatory immunity

Protocol Title: Mechanism and Predictors of Cardiotoxicity after Prostate Cancer Treatment: A Parallel Cohort and Randomized Trial Comparing Radiation Alone, Radiation plus Leuprolide, and Radiation plus Relugolix

contributes to ADT-related CV toxicity, as well as identifying biomarkers that may predict individuals at heightened risk of adverse CV events from ADT, and thereby benefit from cardiac risk-reducing relugolix.

Subaim 2.1: To determine how proteomic biomarkers associated with inflammatory immunity correspond with CV toxicity following ADT.

We will conduct in-depth proteomic profiling, which has previously been utilized and validated to identify signatures associated with inflammatory immune responses and cardiovascular risk^{50,51}. To evaluate whether these signatures are associated with CV toxicity following ADT using leuprolide but not relugolix, pre-treatment and 12-month post-ADT PBMC will be subjected to proteomic profiling in conjunction with the Emory Integrated Proteomic Core as published by our colleagues at the Winship Cancer Institute⁵².

Aim 3: To determine how pre-existing genomic alterations promoting inflammatory immunity impact development of CV toxicity following GNRHa versus relugolix.

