Numerous genetic alterations have been shown to result in either enhanced or diminished ability to mount inflammatory immune responses, including genes associated with 'clonal hematopoiesis of indeterminate potential' (CHIP) such as DNMT3A, TET2, ASXL1, PPM1D, KDM6A, and BCOR⁵³⁻⁵⁵, as well as several others that alter inflammatory immune function⁵⁶⁻⁶². The impact of these immune-related genomic alterations on the development of inflammatory immunity and CV toxicity following ADT will be examined in Aim 3, testing the underlying hypothesis that **somatic mutations associated with enhanced effector responses lead to increased CV injury in men receiving GNRH agonists but not relugolix.**

5. Study Intervention/Investigational Agent

Hormone Therapy Intervention

For men who will be receiving ADT with radiation therapy, there will be a 1:1 randomization between GNRHa (i.e. leuprolide or triptorelin) versus oral relugolix. Dosing for these agents are per standard FDA-approved guidelines, and the study has no impact on dose or duration of therapy.

For men receiving GNRHa, standard FDA-approved intramuscular or subcutaneous injectable doses will apply (i.e. leuprolide 7.5 mg monthly, 22.5 mg q3month, 45 mg q6month; triptorelin 11.25 mg q3month, 22.5 mg q6month). Each patient may receive 21-30 days of oral bicalutamide 50 mg daily beginning at the time of first injection (i.e. to hinder the initial testosterone flare associated with GNRHa) at the discretion of the treating provider. Duration of therapy will depend on the risk category of prostate cancer, as detailed in section 6.

For men receiving oral relugolix, standard FDA-approved oral doses will apply (i.e. 360 mg on day 1, followed by 120 mg daily for the duration of therapy). The tablet is in doses of 120 mg, and it can be taken by mouth with or without food. If the subject misses > 7 days of medication, then a loading dose of 360 mg will be initiated followed by re-initiation of 120 mg daily thereafter. Participants will be asked to complete a drug diary and bring the diary in addition to medication for reconciliation at each follow up visit. Duration of therapy will depend on the risk category of prostate cancer, as detailed in section 6.

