Analysis Plan: We will measure coronary plaque volume using CCTA images at both baseline and 12-months post-treatment initiation. The primary endpoint will be (1) total coronary plaque volume (continuous). Secondary endpoint will be non-calcified coronary plaque volume (continuous). Other outcome measures include (1) calcified plaque volume (continuous), (2) low-attenuation plaque volume (continuous), (3) coronary artery calcification score (continuous), and (4) coronary vessel stenosis (ordinal). The change in endpoint metrics between baseline and 12-month will be estimated for leuprolide versus relugolix versus no ADT. Data transformation to fit statistical assumptions will be done as needed. In addition, we will implement multivariable models that control for potential confounders (e.g. age, statin medication use) using general linear regression and/or logistic regression.

Power: We hypothesized that there will be significantly greater total plaque burden (i.e. summation of total plaque volume of all major coronary territories) increase from baseline to month 12 following GNRHa versus no ADT or relugolix. Using a standard deviation of 30 mm³ for the change in total plaque volume from scans obtained at two time points approximately 12 months apart in the study, 60 participants (30 in each comparative treatment arm) with both baseline and month 12 CCTA would provide 80% power to detect a difference of ≥ 20 mm³ in the change in total plaque volume [$P(X>Y) 0.72$] from baseline to 12 months.

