Aim 2.2: To determine how proteomic biomarkers associated with inflammatory immunity correspond with CV toxicity following ADT, we will conduct in-depth proteomic profiling, which has previously been utilized and validated to identify signatures associated with inflammatory immune responses and cardiovascular risk^{50,51}. To evaluate whether these signatures are associated with CV toxicity following ADT using leuprolide but not relugolix, pre-treatment and 12-month post-ADT PBMC will be subjected to proteomic profiling in conjunction with the Emory Integrated Proteomic Core as published by our colleagues at the Winship Cancer Institute⁵². Using nanocapillary liquid chromatography coupled with tandem mass spectrometry, this technology will be used to analyze patient PBMC samples for highly sensitive protein identification, posttranslational site mapping, and protein quantification. Briefly, PBMCs will be thawed under controlled conditions, sonicated in the presence of lysis buffer, protease inhibitors and phosphatase inhibitors. Protein samples will be sequentially digested, desalting, and dried under vacuum. Following reconstitution, samples will be loaded and eluted from a silica column driven by a UPLC system, monitoring elution spectra on a Fusion Mass Spectrometer. The mass spectrometry scans will be collected at a resolution of 120,000 at m/ 200 in profile mode while in a higher-energy collision dissociation fragmentation MS/MS spectra. Following sequencing, the combined *Homo sapiens* UniProt subsets will be used as references for proteomics searches. Data will be normalized to account for systematic differences in protein signal distributions, by aligning the medians of the log₂ protein signal distributions. Pathway enrichment will be conducted using gene sets obtained from the KEGG Pathway and MSigDB databases.

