Analysis Plan: The correlation among baseline genomic biomarkers, inflammatory biomarkers, and proteomic biomarkers will be described using Spearman Correlation Coefficient for all patients and by treatment group separately. The association of genomic alterations with CV injury metrics (as defined in Aim 1) will be handled by similar statistical strategy as in Subaim 1.2. Additionally, the association of genetic aberrations with peripheral immune responses (as in Aim 2) will be carried out by similar statistical strategy as in Aim 2.

Other statistical considerations:

Safety Population: All patients receiving at least one dose of GNRHa or Relugolix (for parallel randomized arms) or radiation alone (for parallel single cohort arm) will be considered evaluable for safety analyses.

Intent-to-Treat Population: Patients who are evaluable for safety and who are furthermore evaluable at 12-month CCTA assessment will be considered evaluable for correlative biomarker analyses.

Safety Analysis: All AEs experienced data will be described by summary statistics. Adverse events will be assessed according to CTCAE version 5.0 and will be evaluated by grade, attribution, and organ class. Adverse event listings and tabulated summaries of categorized AEs will be generated for all patients collectively and will be summarized by arms. Vital signs and laboratory data will be summarized for changes over time on study.

Stopping Rule: The two ADT test agents are FDA-approved drugs that are used in clinical practice, and hence no stopping rule for safety is in place officially.

7. Data Specimen Banking

To achieve Aims 2 and 3 discussed above, peripheral blood specimens will be collected longitudinally four times for each enrolled patient (i.e. pre-treatment, 3 months, 6 months, 12 months).

Draw 1 (pre)	Draw 2 (3mo)	Draw 3 (6mo)	Draw 4 (12mo)
Pre-ADT	2-4 months post-ADT initiation	6-8 months post-ADT initiation	12-15 months post-ADT initiation

The blood is collected and processed according to the standard operating practices and regulatory parameters of the Winship biorepository and under the guidance of a board-certified pathologist.

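### Aims 2 and 3 hypothesise a marker–injury link under GNRHa but not relugolix, yet no stated analysis tests whether that link differs by arm

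*Combined protocol and SAP*

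**What the plan says.** **Hypotheses.** Section 4, Aim 2 states that "pre-existing inflammatory immunity increases the risk of CV injury following ADT due to an immune-mediated effect of GNRHa but not antagonists". Section 4, Aim 3 states that mutations linked to enhanced effector responses "lead to increased CV injury in men receiving GNRH agonists but not relugolix". The proteomic question in Section 6, Aim 2.2 is posed the same way: "To evaluate whether these signatures are associated with CV toxicity following ADT using leuprolide but not relugolix".

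**Analyses (Section 6).**
- The Analysis Plan following Aim 2.2 tests biomarker change between treatment groups by Kruskal-Wallis. It then links that change to the Aim 1 CV injury metrics by the Aim 1.2 strategy, with Holm-Bonferroni adjustment.
- The Analysis Plan following Aim 3 describes Spearman correlations among genomic, inflammatory and proteomic biomarkers "for all patients and by treatment group separately". The association of genomic alterations with CV injury "will be handled by similar statistical strategy as in Subaim 1.2".
- The Aim 1 Analysis Plan contains the only regression written out: "multivariable models that control for potential confounders", with age and statin use as examples, by general linear and/or logistic regression.

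Subaim 1.2 appears only as a row title in the Section 9 timeline. No method is given for it.

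**The concern.** Each hypothesis has the same form: the slope of CV injury on a marker, or the carrier versus non-carrier difference, is present in one randomised arm and absent in the other. Only a direct comparison of the two slopes can support that. A pooled main effect cannot, and neither can a significant result in one arm beside a non-significant result in the other, because the two results may differ by sampling error alone.

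Section 4 says that Aim 2 should help identify men at heightened risk who would benefit from relugolix. If a marker predicts plaque growth equally under both drugs, it is prognostic and gives no reason to prefer one drug over the other on the strength of the marker. The plan as written has no step that separates that case from a truly arm-specific predictor.

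**Working it through.** **1. Which stated analysis compares the marker–injury link between arms?**

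| Stated analysis | What it compares | Tests whether the link differs by arm? |
|---|---|---|
| Kruskal-Wallis (Aim 2) | Biomarker change between groups | No; the outcome is the biomarker |
| Link to CV injury (Aims 2 and 3) | Marker with injury, by the Aim 1.2 strategy | Not specified; the strategy is unwritten |
| Spearman (Aim 3) | Biomarkers with each other, overall and by group | No; descriptive, and injury is not included |
| Aim 1 regression | Endpoint change, adjusted for confounders | No interaction named |
| Holm-Bonferroni (Aim 2) | Adjusts the tests performed | No; adds no contrast |

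No arm-by-marker term, and no comparison of within-arm associations with injury, appears anywhere.

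**2. Inputs.** From the Section 6 power statement: 30 men per arm and an SD of 30 mm³ for the change in total plaque volume. From Section 6, Aim 2.1: 71 plasma factors. From Section 3: CHIP in 10–20% of people over 70, which if applied to this trial (an assumption) gives 3–6 carriers per arm. Correlations and carrier effects are assumptions, because the documents give none.

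The only power figure in the documents is 80% for Aim 1. The normal approximation gives Φ(20/(30√(2/30)) − z), which is 73.3% at two-sided 5% and 82.6% at one-sided 5%; alpha and sidedness are not stated. No power is given for Aims 2 and 3.

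**3. Chance of a GNRHa-only pattern when the arms are alike.** Suppose, for illustration, that each arm is tested separately. With the same true association and equal, independent arms, let p be the within-arm power. Then

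P(significant in GNRHa, not significant in relugolix) = p(1−p), with maximum 0.25 at p=0.5.

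For a continuous marker, Fisher's z gives p ≈ Φ(atanh(r)·√27 − z), plus a negligible opposite tail except near r=0. Example, r=0.3: 0.3095 × 5.196 = 1.608; Φ(1.608 − 1.960) = 0.36; 0.36 × 0.64 = 0.23. A simulation of 100,000 trials agrees closely:

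| Common r | p at 5% | p(1−p) | Simulated, 5% | Simulated, 0.05/71 (first Holm step) |
|---|---|---|---|---|
| 0 | 0.05 | 4.75% | 5% | 0.1% |
| 0.2 | 0.18 | 15% | 15% | 1% |
| 0.3 | 0.36 | 23% | 23% | 3% |
| 0.4 | 0.60 | 24% | 24% | 10% |
| 0.5 | 0.81 | 15% | 14% | 20% |
| 0.6 | 0.95 | 5% | 4% | 24% |

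The 25% maximum at unadjusted 5% falls near r=0.36. Holm moves the peak to stronger correlations and does not remove it.

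For carriers against non-carriers (t-test simulation, SD 30 mm³, same effect in both arms), effects of 20, 30, 40 and 60 mm³ give 15%, 23%, 25% and 10% with 3 carriers per arm, and 21%, 25%, 16% and 1% with 6.

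**4. The interaction test on the same data.** False differences occur in about 5% of trials throughout, in either direction combined (simulated 4.8–5.2%).

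Its power is limited. The detectable difference in Fisher z at 80% power and two-sided 5% is (1.960 + 0.842) × √(2/27) = 0.76, so r = tanh(0.76) = 0.64 against 0. At r = 0.3, 0.4, 0.5 and 0.6 against 0, power is 21%, 34%, 52% and 72%. For carrier effects of 20, 30, 40 and 60 mm³ against none, it is 12%, 21%, 33% and 63% with 3 carriers per arm, and 17%, 33%, 53% and 86% with 6. All of these are unadjusted.

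**The case against.** A reader might infer that the plan prescribes separate significance tests of marker against plaque in each arm, and so carries an error rate near 24%. The documents do not say that. The by-group analysis in the Aim 3 plan is descriptive, is confined to correlations among biomarkers and leaves plaque out. For CV injury the strategy is simply unwritten. By-arm testing is a likely reading of hypotheses in this form, but the percentages above belong to that reading and not to a stated procedure.

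A reader might also infer that Aim 2 has no between-arm test. It has one: Kruskal-Wallis addresses whether immune response differs by drug, which is the question in Aim 2's title. It does not address whether the marker–injury link differs. Nor does the Aim 1 regression text exclude interactions; it is silent on them.

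Holm adjustment matters too. At the 71-marker threshold the pattern falls to 3% at r=0.3 and 10% at r=0.4, so the unadjusted figures should not be quoted alone.

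Finally, Section 2 describes Aim 2 as secondary, laboratory-based correlative work, and Section 1 makes the genomic question a secondary objective. That limits the severity. It does not close the gap, because Section 4 says that these hypotheses are to be tested.

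These points govern how the concern is sized. None supplies the missing comparison.

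**Conclusion.** The omission stands: the plan as written cannot support a conclusion that a marker or mutation matters under GNRHa and not under relugolix. A pooled analysis would not test the hypotheses.

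Under separate by-arm testing, a spurious GNRHa-only pattern has a ceiling of 25% per marker that is equally predictive in both arms. It ranges from about 4% to 25% over r=0 to 0.6 at unadjusted 5%, and from about 0.1% to 24% at the first Holm step for 71 markers. The formula p(1−p) rests on independent arms with equal power. The individual percentages also rest on assumed correlations, carrier counts and carrier effects, and on 30 evaluable men per arm.

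Confidence is high in the omission, and lower in any single error rate. The plan should be changed, but Aim 1's primary comparison is unaffected.

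**What to change.** In the Aim 2 and Aim 3 analysis plans, replace the reference to Aim 1.2 with a written model, fitted in the men randomised to GNRHa or relugolix:

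change in total plaque volume ~ arm + marker (or carrier status) + arm × marker + baseline plaque volume + ASCVD stratum.

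- Specify the analogous model for the other Aim 1 CV injury metrics, including one suited to the ordinal stenosis grade.
- Place the interaction tests in a defined Holm family. Without one, 71 markers at 5% would yield 71 × 0.05 ≈ 3.6 expected false interactions.
- Base every statement that an effect is present under GNRHa and not under relugolix on the interaction estimate with its 95% CI.
- Label by-arm results and the no-ADT cohort as descriptive.

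The cost is analysis-plan wording only; no extra patients, scans or samples are needed. The drawback is imprecision. A continuous marker needs about r=0.64 against 0 for 80% power even before adjustment, and with 3–6 carriers per arm power for mutations is low unless effects are large. Fewer arm-specific claims will be possible, and the plan should say so.

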Men with localized intact PCa, or non-metastatic recurrence following prostatectomy, and prescribed radiation therapy (XRT) with or without concomitant ADT will be consented and enrolled on this prospective trial. Eligible subjects are men > 18 years old diagnosed with non-metastatic PCa planning to undergo curative-intent therapy. Men with prior cardiac stent or bypass surgery will be excluded. Men with prior exposure to ADT will be excluded.

Each patient will undergo external beam XRT with or without concomitant ADT of 6-24 months duration. **For those men with National Comprehensive Cancer Network (NCCN)-defined unfavorable intermediate- or high-risk disease, or with biochemically recurrent PCa requiring salvage XRT plus ADT, each will be randomized 1:1 between injectable intramuscular or subcutaneous GNRHa depot (leuprolide 22.5 mg every 3 months, leuprolide 45 mg every six months) versus GNRH-antagonist (oral relugolix 360 mg loading dose followed by 120 mg daily).** Men with NCCN-defined low- or favorable intermediate-risk intact disease, or those with biochemically recurrent PCa requiring salvage XRT without ADT, will be treated with XRT alone. Each patient will provide consent for (1) pre-treatment and 12-month post-ADT prospective ECG-gated, contrast-enhanced CCTA and (2) peripheral blood banking at baseline and at 3-, 6-, and 12-months post-treatment (**Figure 5**).

Figure 5. Study Schema

ADT randomization will be created using preconstructed allocation sequences using maximal randomization (<https://ctrandomization.cancer.gov/tool/>). Patients will undergo a pre-randomization stratification based on Atherosclerotic Cardiovascular Disease (ASCVD) risk score (low/intermediate versus high). All principal investigators and co-investigators will be blinded to this randomization block. Lead statistician ([name]) and clinical research coordinators will have access to this allocation sequence.

Methods: As seen in above study schema, each patient in each cohort will undergo pre-treatment and 12-month post-ADT initiation coronary CT. Each patient will undergo a non-contrast CT scan using standard

Protocol Title: Mechanism and Predictors of Cardiotoxicity after Prostate Cancer Treatment: A Parallel Cohort and Randomized Trial Comparing Radiation Alone, Radiation plus Leuprolide, and Radiation plus Relugolix

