Based on current prostate cancer volume at Winship Cancer Institute, accrual is expected to be complete in 12 months. Specifically, approximately 40 new patients with localized intact or recurrent PCa eligible for XRT (with or without ADT) are seen at all Winship sites monthly. We predict an enrollment rate of 20% with a low dropout rate, given that the final blood draw and coronary CT will occur 12 months after treatment initiation, which corresponds to the time of first or second standard post-treatment follow up appointment after completion of therapy.

Clinical research coordinators will screen all prostate cancer radiation oncology providers (directed by PI [name]) for all eligible patients to enroll. Co-investigators will be responsible for consenting patients in radiation oncology clinic.

13. Recruitment Methods

Patients will be recruited from those seen at the Department of Radiation Oncology at Winship Cancer Institute (EUH, EUHM, ESJH, EPTC). A brief description of the study will be given verbally to the patients, followed by written informed consent, and any relevant supplemental material as needed. The patients will be given ample time to review the consent and a time for questions and answer will be provided.

Study Enrollment Procedures

A copy of the institution's IRB-approved informed consent document and written justification for any changes made to the informed consent for this protocol must be on file at the Online Collaborative Research Environment (OnCore, <https://oncore.emory.edu>) and available to the Emory University Office for Clinical Research) before any patients may enter. The Winship Cancer Center institution consent form must be reviewed and approved and all documents must be received (i.e., IRB approved documentation, IRB approved consent form, etc.).

Patient Registration

All patients entering this study will be registered with the Clinical Trials Office (CTO) at the Winship Cancer Institute, Atlanta, GA. The CTO is open Monday through Friday from 8am-5pm (EST). OnCore will be used to record information for all registered patients including their assigned patient ID.

Study personnel will notify Winship Central Subject Registration (WCSR) by email at [contact], once subject has been consented for a trial.

Email notification must be done within 24 hours after consent has been obtained and it will include scanned copies of:

- Signed patient consent form
- HIPAA authorization form

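### Planned ADT duration (6–24 months) is ignored in randomisation and in the Aim 1 analysis, so the 12-month plaque contrast averages over mixed exposure and may be diluted

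*Combined protocol and SAP*

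**What the plan says.** **Exposure.** Section 6 (Procedures Involved): "Each patient will undergo external beam XRT with or without concomitant ADT of 6-24 months duration". Section 5 (Study Intervention) adds that "the study has no impact on dose or duration of therapy" and that "Duration of therapy will depend on the risk category of prostate cancer, as detailed in section 6". Section 6 then gives only the overall range, with no duration for each risk category.

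**Outcome timing.** Under Methods in section 6, "each patient in each cohort will undergo pre-treatment and 12-month post-ADT initiation coronary CT". That is one baseline and one post-baseline reading. Section 12 says that the final scan "corresponds to the time of first or second standard post-treatment follow up appointment after completion of therapy". Therapy may mean radiation there, so this sentence does not establish who is off ADT at the scan.

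**Allocation.** Section 5: "there will be a 1:1 randomization between GNRHa (i.e. leuprolide or triptorelin) versus oral relugolix". Section 6: "Patients will undergo a pre-randomization stratification based on Atherosclerotic Cardiovascular Disease (ASCVD) risk score (low/intermediate versus high". No other stratification factor is named.

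**Analysis.** The Aim 1 Analysis Plan in section 6 says: "The change in endpoint metrics between baseline and 12-month will be estimated for leuprolide versus relugolix versus no ADT". Age and statin use are the example covariates. No subgroup, sensitivity analysis or handling rule is given for men whose ADT ended before the scan. The analysis population defined under Other statistical considerations does not depend on ADT status at the scan.

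**The concern.** Planned duration follows cancer risk category, so it can be known before allocation. It also fixes how much of the 12-month window is spent on drug. The protocol itself treats duration as relevant to harm: section 16 lists shortening concomitant ADT among the ways to limit treatment-related morbidity in high-risk men. Yet the primary contrast pools men exposed for about half the window with men exposed for all of it, and nothing in the plan separates them.

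What is at stake is interpretation. The trial is meant to explain a mechanism. If the 12-month difference is small, the planned analysis cannot suggest whether GNRHa has little effect on plaque or whether shorter exposure pulled the average down. If a difference appears, the analysis cannot say whether it depends on continued exposure.

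**Working it through.** **Inputs from the documents.** ADT duration is 6–24 months and the scan is 12 months after initiation (section 6). There are 30 men per arm, the SD of change is 30 mm³, the difference is 20 mm³ and power is 80% (section 6, Power). Alpha, sidedness and test are not stated.

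**Assumed inputs.** *f* is the share of men on short courses. *r* is the fraction of the full 12-month effect that a short-course man shows at 12 months. The documents give neither. All short courses are taken as 6 months, the shortest allowed, so longer ones would lose less.

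**1. The plan's own power.** For a two-sample t-test, the noncentrality is (20/30) × √(30/2) = 2.58 on 58 degrees of freedom.
- One-sided 0.05: 81.8% (simulated Mann-Whitney 80.4%).
- Two-sided 0.05: 71.9%.

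With these inputs the stated 80% is reached at one-sided 0.05 but not at two-sided 0.05. Two-sided power is used below, so the reference is 72%.

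**2. Time off drug at the scan.** This is 12 minus duration: 6 months for a 6-month course and 0 for a 12-month course. Longer courses are still running.

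**3. Expected difference.** Treat 20 mm³ as the full-exposure effect, with no effect under relugolix. Then Δ = 20 × [1 − f(1 − r)].

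| | f = 25% | f = 50% | f = 75% |
|---|---|---|---|
| r = 1 (early effect persists) | 20.0 | 20.0 | 20.0 |
| r = 0.75 | 18.75 | 17.5 | 16.25 |
| r = 0.5 (accrues only on treatment) | 17.5 | 15.0 | 12.5 |
| r = 0.25 (part of the effect lost after stopping) | 16.25 | 12.5 | 8.75 |

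**4. Power for the r = 0.5 row** (t-test, two-sided 0.05, SD 30, 30 per arm; noncentrality = Δ/30 × √15).
- 17.5 mm³: noncentrality 2.26, power 60.3%.
- 15.0 mm³: noncentrality 1.94, power 47.8%.
- 12.5 mm³: noncentrality 1.61, power 35.5%.

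A normal approximation that adds the extra between-patient variance in the GNRHa arm gives 61.3%, 48.5% and 36.1%.

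**5. Chance imbalance.** Take f = 50% and a fixed 30/30 split. A gap of at least 6 short-course men between arms has probability of about 20%. For 18 versus 12, with r = 0.5:
- GNRHa mean exposure is (18 × 6 + 12 × 12)/30 = 8.4 months, so the contrast is 20 × 8.4/12 = 14 mm³ instead of 15, a shift of 1 mm³.
- If both agents shared a 20 mm³ per 12 months effect, the relugolix mean exposure would be (12 × 6 + 18 × 12)/30 = 9.6 months, or 16 mm³. The shift is then 14 − 16 = −2 mm³.
- The standard error of the contrast is 30 × √(2/30) = 7.7 mm³.

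**6. Precision within a level.** At f = 50% there are about 15 men per arm in each level. The standard error is 30 × √(2/15) = 11.0 mm³ and the 95% half-width is about 22 mm³. Two-sided power for 20 mm³ is 42%, below the 48% for the whole comparison at a diluted 15 mm³. The difference between levels has a standard error of 11.0 × √2 = 15.5 mm³, against an expected 20 − 10 = 10 mm³ under r = 0.5.

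**The case against.** The strongest reply is that comparing two agents as prescribed, at a fixed time from initiation, is a legitimate pragmatic estimand, and that randomisation balances duration in expectation. That stands. A reader might infer that the contrast is confounded by duration; it is not.

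A second reply concerns the biology. A reader might take the hypothesis to be an effect present only while on drug, with recovery afterwards. The documents do not say so. Section 2 speaks of early toxicity. In section 3 a direct effect is contrasted with slow metabolic change, and events are cited after 3–6 months of therapy and from 4 weeks. A 6-month course could deliver such an effect in full, and nothing is said about plaque after stopping. Dilution is therefore possible but not established. The 20 mm³ may also already be the average expected in the enrolled mix, in which case reducing it again would discount twice.

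Third, chance imbalance in duration is a weak argument. Even a 6-man gap moves the contrast by 1–2 mm³ against a standard error of 7.7 mm³, and the test's error rate already covers chance imbalance.

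Fourth, the covariates in Aim 1 are only examples, so duration could be added. That is true, but the plan does not commit to it. The trial is open-label and the study does not fix duration, so only a value recorded before allocation is certain to be independent of arm.

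**Conclusion.** The plan leaves a mixed-exposure estimand undescribed and makes no use of a baseline variable that would help interpret it. This is worth correcting because the change is cheap, not because the primary contrast is invalid.

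The possible loss runs from none (an early effect that persists, or 20 mm³ already being the mixed average) to a difference of 17.5–12.5 mm³ with two-sided power of roughly 60–35%. That lower range requires accrual only during treatment, 20 mm³ as the full-exposure effect, and 25–75% of men on 6-month courses. If part of the effect were lost after stopping, the reduction would be larger. The documents do not say which case applies.

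Two stronger readings are not supported: that duration biases the randomised comparison, and that men still on treatment at 12 months should supply the main test. At a 50% share, that subgroup has less power than the whole comparison even after dilution.

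**What to change.** 1. Record intended ADT duration before allocation, in two levels: planned course ends before the 12-month CCTA, or continues to or past it. Define in advance how 12-month courses are classed and how depot coverage counts, since one arm receives injections covering up to 6 months and the other a daily tablet.
2. Add this as a second stratification factor beside ASCVD risk. For men already randomised, use baseline cancer risk category as the covariate, because it predates allocation and is said to determine duration.
3. Include the factor in the Aim 1 model for GNRHa versus relugolix. Keep the whole randomised comparison as primary.
4. Report the contrast by planned duration as a prespecified supportive result, labelled imprecise.
5. Reconcile section 5, which refers to section 6 for duration by risk category, with section 6, which gives only the range.

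The cost is one field before randomisation, one model term, four strata instead of two in 60 men, and wide within-level intervals (about ±22 mm³ at a 50% share). These estimates will help describe whether the result varies with exposure, but they will not settle it. No extra patients, scans or visits are needed, and no man's treatment duration changes.
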